1.2 Hypotheses

1.2.1: Compared to TAU: MBCT-S subjects will experience a longer duration from baseline until a suicide event.

1.2.2: Compared to TAU: MBCT-S subjects will experience a greater decrease in suicide events during the study period.

1.2.3: Compared to TAU, MBCT-S subjects will experience a longer duration from baseline until a suicide attempt.

1.2.4: Compared to TAU: MBCT-S subjects will have lower scores on the Beck Scale for Suicide Ideation, the Beck Depression Inventory and the Beck Hopelessness Scale.

2. Background and Significance

Strategies for reducing the risk of suicide are a top priority within the VA. Every month the VA becomes aware of approximately 1,100 veterans in VA care who attempt suicide. Although VA suicide prevention efforts seem to improve safety for some groups of veterans, VA data show that 11% of veterans with one suicide attempt make a re-attempt within 9 months.

There is a significant gap in the availability of evidence-based psychotherapies targeting suicide. While the VA has implemented most components of the multifaceted prevention approach recommended in a 2009 VA report on suicide,¹ it has yet to implement nationally any evidence-based psychotherapies targeting suicide. This gap may be due, in part, to the dearth of evidence-based therapies addressing suicide. The 2009 VA report, which identified only one small randomized controlled trial (RCT) with veterans and a handful with non-veterans, cited the pressing need for high-quality RCTs testing specialized therapies for those at suicide risk, a recommendation reiterated in a 2011 report commissioned by the Suicide Prevention Resource Center (SPRC),² which cited a "desperate" need for suicide-focused therapies.

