Of the handful of RCTs for suicide therapies conducted to date, cognitive behavior therapy (CBT) has emerged as the most promising approach³. The psychotherapy to be studied in the current RCT, Mindfulness-Based Cognitive Therapy for Suicide Prevention (MBCT-S),³ is a CBT approach that builds on an existing psychotherapy targeting depression, Mindfulness-Based Cognitive Therapy (MBCT). Both interventions integrate CBT approaches with "mindfulness," a Buddhist meditation technique found helpful in managing emotional dysregulation and other psychological processes underlying depression and suicidality. The investigators have adapted MBCT-S for suicide prevention by incorporating the VA's Safety Planning intervention and other mindfulness-based techniques specifically geared to addressing suicide risk. A short-term (8-week) group intervention, MBCT-S is cost-efficient, compatible with current VA suicide prevention strategies holds the promise of substantially reducing suicide risk in VAconnected veterans.

3. Research Design and Methods

Using a randomized controlled study design, the study will randomize 164 participants to receive either MBCT-S+TAU (n=82) or TAU only (n=82) in order to compare the adjunctive value of MBCT-S to the enhanced care currently provided to high risk for suicide patients. All consenting veterans meeting eligibility criteria will be enrolled in the study during the inpatient psychiatric admission associated with serious suicide ideation or a suicide attempt. As described in detail below, we will use broad inclusionary criteria in order to obtain a sample of patients who are diagnostically representative of those on the HRSL. Participants will receive a total of 5 assessments: (a) baseline (Time 1); (b) 4 weeks post-baseline (mid-treatment) (Time 2); (c) 8 weeks post-baseline (coinciding with MBCT-S treatment completion) (Time 3); (d) 6-months post-baseline (Time 4); and (e) 12-months post-baseline (Time 5). A 12-month follow-up will provide information on key outcomes that occur infrequently, such as suicide attempts,

and thus require a wider window for detection. In addition, data on suicide events and attempts will be obtained from patients' medical records at 12 months post-baseline *to verify self-report data*. We will use an intent-to-treat analysis to compare intervention and control group participants at each time frame.

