3.3 Sample Size Justification & Subject Selection

The study will enroll a total of 164 subjects hospitalized on the **second** and **second** acute psychiatric units who qualify for inclusion on the VA's High Risk for Suicide List (HRSL). The study will only sample HRSL patients who experienced a hospitalization as a result of their index suicide event, which represents approximately 77% of all active HRSL patients. Approximately 8-10 patients are admitted to the acute units for suicide risk monthly. Over an approximately 36-month recruitment period, we expect to recruit approximately 3-5 patients per month to meet our enrollment goal.

Because our inclusion criteria are broad, we expect our sample to be representative of the population of HRSL patients hospitalized on the acute units. In FY 2011, this population was 85% male, 52% Caucasian; 33% Black; 8% Latino; and 4% Asian. The mean age was 47 (range=23 to 95). These veterans were diverse in terms of psychiatric diagnoses (non-mutually exclusive diagnoses include Depression-60%; PTSD-47%; Drug-related disorders-40%; Alcohol-Related disorders-38%; Bipolar Disorder-20%; and Schizophrenia-9%) and service era (Vietnam Era-29%; Post-Vietnam-25%; Gulf War-13%; OEF-OIF-25%).

To detect group differences on our principal measure, duration of time to first suicide event, we based our power analysis on prior literature and pilot data. Using the stpower cox command in Stata/MP 12.1 for Windows, which follows Hsieh and Lavori, ⁴ our power analysis estimated the required sample size to achieve 80% power at a 0.05 alpha level at a pre-attrition recruitment of 164 participants evenly

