We will also employ methods to examine the possible effects of both therapist and site on study outcomes by testing for nesting effects in our models. For the therapist variable, we will use a partially nested design₁₁, since therapist effects will be analyzed for treatment group participants only. In the case of mixed-effects models, therapist and site variables will be entered as fixed effects since the limited number of therapists and sites in the proposed study (2 each)₁₂ constrains the generalizability of inferences that could be derived from specifying random effects. We have modified the description of our analyses below to specify how we will test for site and therapist effects in each case.

For H1a, survival time analyses to compare MBCT-S to TAU will be run once at 12 months post-baseline using the Cox proportional-hazards regression model to test for group differences in the time from baseline to first in-study suicide event. Site will be entered as a nesting factor into the regression. For the therapist variable, we will test for a partially nested effect, simplifying assumptions regarding the patterns of clustering related to the use of a primary therapist or primary group. The regression analysis will also allow us to control for censoring effects due to the differential length of follow-up or the completion of follow-up without a repeat suicide event. However, if the proportional hazard assumption is not met, we will utilize other approaches to survival analysis, such as the log-rank test.

For H1b, we will obtain a count of "suicide events" during each assessment period, including baseline. Given that suicide events occur infrequently and have a non-normal distribution, a mixed-effects Poisson regression will make a between-group comparison with events as the dependent variable, one between-group variable (MBCT-S vs. TAU), one repeated factor for the multiple assessments, and a group by time interaction. The model will specify intra-subject correlation as a random effect nested within site (which will be specified as a fixed effect) and we will test for a partially nested effect for therapist as specified above. We will consider several correlational structures between repeated measures (e.g., compound symmetry) and determine the best structure using the Akaike's Information Criterion (AIC). Potential confounders that meet the p<0.10 criterion stated above will be entered as covariates.

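### H1b treats the baseline event count as a Poisson outcome although most participants are enrolled because of an index event, so the model-based standard error for hypothesis 1.2.2 cannot be relied on

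*Combined protocol and SAP*

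**What the plan says.** Hypothesis 1.2.2 states that, compared with TAU, "MBCT-S subjects will experience a greater decrease in suicide events during the study period". The matching analysis is H1b in section 5. It takes the event count "during each assessment period, including baseline" as the dependent variable of a mixed-effects Poisson regression with a group term, "one repeated factor for the multiple assessments, and a group by time interaction". On variance it says: "The model will specify intra-subject correlation as a random effect nested within site". Several correlation structures are to be compared by AIC, with compound symmetry as the only example. No overdispersion term, period-specific variance or robust standard error is named, and the look-back period for the baseline count is not defined.

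On entry, section 3 enrols patients "during the inpatient psychiatric admission associated with serious suicide ideation or a suicide attempt", and section 3.3 adds: "The study will only sample HRSL patients who experienced a hospitalization as a result of their index suicide event". Other text is looser. Criterion 3.4.1b also admits patients already on the high-risk list whose admission related to ideation or behaviour, whereas section 4.2 counts ideation as an event only when it comes with intent. The amendments of 1-24-14, 5-8-14 and 7-22-14 admit some patients without current ideation, drop the flag requirement and add outpatients. The last of these keeps a focus on a recent event or crisis.

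**The concern.** A baseline count that is at least 1 for most people because of how they were recruited is not a draw from each person's own event rate. A Poisson model with one random intercept shared by baseline and follow-up makes two errors with such data. It charges Poisson noise to baseline counts that hardly vary, which makes the standard error too large. It also cannot absorb differences between people in follow-up counts that the baseline count does not share (a few people with repeated events), which makes the standard error too small. Which error dominates depends on how many participants repeat, and the documents do not say. H1b is the only planned test of hypothesis 1.2.2, so its false-positive rate would depend on an unknown nuisance quantity.

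**Working it through.** **The plan's own figure.** The only sample-size figure is for H1a (sections 3.3 and 5). With hazard ratio 0.421, covariate SD 0.5, 80% power and two-sided 0.05, events = (1.960 + 0.842)² / (0.25 × ln(0.421)²) = 41.9. Then 41.9/0.321 = 131 (stated 132), and 131/0.80 = 164 (stated 164). It reproduces. There is no power or variance figure for H1b.

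**Inputs for H1b.** From section 3.3: 82 per arm, and 32.1% of controls with any event in 12 months. Assumed: everyone has exactly one baseline event, and follow-up counts are Poisson with a gamma person-level multiplier of variance θ (the frailty variance), scaled so that 32.1% have an event at every θ.

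**Step 1, what the model uses.** With complete data, a shared random intercept and a full group-by-time term, the intercept drops out of the within-person contrast. The interaction test becomes the likelihood-ratio test on the table of event totals by arm and time; a quadrature fit of the mixed model gave the same statistic (0.0994). For baseline versus follow-up (1 df), the model variance is 1/B1 + 1/F1 + 1/B0 + 1/F0, where B and F are baseline and follow-up totals per arm. Under the null this is 2/F + 2/B.

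**Step 2, the true variance.** With fixed baseline counts only follow-up varies: 2φ/F, where φ = 1 + θμ and μ is the mean follow-up count. Since B = 82 and F = 82μ, model SE / true SE = √[(1 + μ)/(1 + θμ)]. The model is too cautious below θ = 1, right at θ = 1 and too liberal above it.

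**Step 3, numbers.** μ = −ln 0.679 at θ = 0, otherwise (0.679^(−θ) − 1)/θ. Type I error (1 df) = 2[1 − Φ(1.96 × ratio)]. The last two columns are from 6,000 simulated trials per row.

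| θ | μ | Model SE / true SE | Type I, 1 df (formula) | Type I, 1 df (simulated) | Type I, five times, 4 df (simulated) |
|---|---|---|---|---|---|
| 0 | 0.387 | 1.18 | 2.1% | 2.0% | 5.4% |
| 0.5 | 0.427 | 1.08 | 3.4% | 3.1% | 6.6% |
| 1 | 0.473 | 1.00 | 5.0% | 5.0% | 6.8% |
| 2 | 0.585 | 0.85 | 9.4% | 9.4% | 8.8% |
| 4 | 0.926 | 0.64 | 21% | 21% | 15.0% |

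A repeat simulation gave 2.3%, 5.8%, 9.7% and 21% (1 df) and 6.0%, 7.0%, 8.8% and 14.9% (4 df) at θ = 0, 1, 2 and 4. As a benchmark, an unselected Poisson baseline sharing the frailty gave 4.7-5.5% (1 df) and 6.0-7.3% (4 df).

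**Step 4, other baselines and sizes (1 df).** A baseline event in only 80% of participants: 2.8%, 8.8% and 20% at θ = 0, 2 and 4. More baseline spread, 1 + Poisson(1): 4.2%, 5.4%, 6.1% and 11.0% at θ = 0, 1, 2 and 4. With 66 per arm: 2.3% and 8.8% at θ = 0 and 2. In every null scenario the mean log rate ratio was within 0.013 of zero.

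**Step 5, separating the remedies (one baseline event each).**
- Baseline kept, subject-level robust variance: 4.3-5.5% for θ = 0 to 2, and 6.6% at 4.
- Baseline dropped, robust variance: the same.
- Baseline dropped, random-intercept Poisson without robust variance: 4-6% for θ = 0 to 2, but about 12% at 4.

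**Step 6, power at an assumed rate ratio of 0.421, 82 per arm.** At θ = 0: 72% for the planned model (1 df), 53% for its 4-df form, and 78% for follow-up counts with robust variance. At θ = 2 the planned 1-df test shows a nominal 79%, against 73% with robust variance.

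**The case against.** The strongest reply is that the planned interaction has five times and 4 df, and for that test selection adds essentially nothing up to θ = 1, one or two points at θ = 2 (8.8% against a benchmark of 6.0-7.3%) and a clear excess only at θ = 4. The 1-df test is itself correct near θ = 1, and nothing in the documents says where this population lies. Both points stand.

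Three stronger readings are tempting, and the documents support none of them. A reader might infer that the fall from baseline carries no information about treatment, or that the estimate is biased. But H1b compares the fall between arms, and the selection is common to both, so it cancels. A reader might take nearly everyone to have a baseline count of about 1; criterion 3.4.1b, the intent requirement in section 4.2 and the amendments do not allow that, although the problem persists at 80%. A reader might also conclude that the baseline row must be deleted to make the test valid. Step 5 shows that a robust variance does that by itself.

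The choice by AIC could also help, since a period-specific variance would remove most of the problem and is not ruled out. It is not named either, and the one structure given as an example is equivalent to the shared intercept.

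**Conclusion.** The point holds as one about the standard error. H1b as written relies on a model-based variance that does not fit a baseline created largely by selection. The model standard error runs from 18% too large to 36% too small over θ = 0 to 4. Type I error runs from about 2% to 21% for the single contrast, and from about 5% to 15% for the 4-df interaction. These ranges rest on the assumed frailty distribution and baseline counts, and are milder if baseline counts vary more. It cannot be said that the error bars will be wrong in this trial, only that nothing in the plan protects them. The treatment estimate and H1a are unaffected.

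**What to change.** In H1b, specify a subject-level robust (sandwich) variance. This is the change that corrects the type I error.

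Preferably also model only post-baseline counts (Times 2-5), with arm as a single rate ratio over follow-up, period as a factor, a person-time offset, and prior attempts (none vs 1+) as a covariate. Reword 1.2.2 to claim a lower rate of suicide events during follow-up. This matches the randomised comparison and avoids spreading the test over 4 df. With near-Poisson counts, power at a rate ratio of 0.421 is about 78%, against 72% for the planned 1-df test. When everyone has exactly one baseline event, the robust variance alone gives the same 78%.

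The cost is wording only. There are two downsides. If counts are overdispersed, nominal power falls to its honest value (79% to 73% at θ = 2). And if participants have further baseline events that reflect their own risk, dropping baseline discards information: with 1 + Poisson(0.25) baseline events sharing the frailty, power at θ = 2 was 78% with baseline kept and 72% without, both with robust variance. Entering the baseline count as a further covariate is a reasonable way to use that information.

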randomized at a 1:1 ratio to 82 per group. Based on our pilot data we assumed a hazard ratio of 0.421 and a control group failure probability of 32.1%; based on a comparable study by Brown et al., which reported an 18% attrition rate at 12 months, we assumed a 20% attrition rate, and used the standard deviation of the covariate of interest, group assignment, of 0.5. As noted, this analysis indicates we will need to recruit 82 subjects per group (total n=164) to attain a sample size of 66 per group (total n=132) after attrition. Moreover, we expect the study will be powered sufficiently to demonstrate clinical significance of the intervention as well. With respect to our main outcome measure, "duration of time to first suicide event," for example, our pilot data indicate the intervention may reduce by more than half the likelihood of a second suicide event within 12 months. This would translate into substantial savings in both human suffering and hospitalization costs.

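### The Poisson model for suicide event counts (H1b) has no exposure term, so its rate ratio can be modestly biased if observed time differs by arm and partly observed windows are kept

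*Combined protocol and SAP*

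**What the plan says.** Hypothesis 1.2.2 (H1b in section 5) concerns the decrease in suicide events over the study. Section 5 takes the count of events "during each assessment period, including baseline" and states that "a mixed-effects Poisson regression will make a between-group comparison with events as the dependent variable". The core terms are "one between-group variable (MBCT-S vs. TAU), one repeated factor for the multiple assessments, and a group by time interaction". The section adds a subject random effect, site as a fixed effect, a partially nested therapist effect, a correlation structure chosen by AIC, and baseline confounders that pass the p<0.10 screen. It mentions no offset, exposure or person-time, and gives no rule for a window that is only partly observed or missed.

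For the Cox model (H1a), the same section says that the regression will "control for censoring effects due to the differential length of follow-up". H1b has no counterpart.

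Four other places bear on observed time:

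- Section 3 schedules assessments at baseline, 4 weeks, 8 weeks, 6 months and 12 months. It also plans a medical-record check at 12 months, described as verifying self-report.
- Section 3.5 plans retrospective chart review for events over 12 months in every enrolled participant.
- Section 3.3 says "we assumed a 20% attrition rate", with no split by arm.
- Protocol Amendments, item 3 (1-24-14), ties Times 2 and 3 to mid- and post-treatment instead of fixed dates. It matches controls in blocks so that the two arms keep the same assessment timeline.

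**The concern.** A Poisson model without an offset compares events per window, not events per unit of time. This does no harm when every participant is observed for the same length of each window, or when the lengths vary alike in both arms. It does harm when one arm is observed for less time: that arm shows fewer events, and the shortfall enters the arm and arm-by-time terms as if it were a treatment effect.

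The time factor does not solve this. If it is categorical, as the word factor suggests, it removes differences between short and long planned windows that both arms share. It does not adjust for early or late interviews, floating Times 2 and 3, or participants who leave part-way through a window. Attendance and dropout could plausibly differ between a group-therapy arm and usual care, and the direction cannot be known in advance. The rate ratio for hypothesis 1.2.2 is what is at stake.

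**Working it through.** **The plan's own figure.** The documents give no sample size, power or rate ratio for H1b. Their only sizing belongs to the Cox analysis, and it reproduces at two-sided alpha 0.05 and 80% power:

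- Events = (1.960 + 0.842)² / (0.5² × (ln 0.421)²) = 41.95.
- 41.95 / 0.321 = 130.7, so 131.
- 131 / 0.80 = 163.75, so 164.

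That figure does not depend on the present point.

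**Inputs for H1b.** From the documents: 82 per arm, 20% overall attrition, and planned windows of about 4, 4, 18 and 26 weeks. These windows follow the section 3 schedule and serve only as an illustration, since Times 2 and 3 now float. Assumed: the split of dropout by arm, a constant dropout hazard, and dropout unrelated to events.

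**All unobserved time scored as zero events.** The expected rate ratio is the true one multiplied by the ratio of mean observed time. With 12-month dropout d, the mean observed fraction of the year is d / (−ln(1−d)).

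| Dropout MBCT-S / TAU | Mean fractions | Multiplier |
|---|---|---|
| 20% / 20% | 0.896 / 0.896 | 1.00 |
| 18% / 22% | 0.907 / 0.885 | 1.02 |
| 15% / 25% | 0.923 / 0.869 | 1.06 |
| 10% / 30% | 0.949 / 0.841 | 1.13 |
| 25% / 15% | 0.869 / 0.923 | 0.94 |
| 30% / 10% | 0.841 / 0.949 | 0.89 |

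The cruder rule that a dropout is seen for half the year agrees: (1 − 0.15)/(1 − 0.05) = 0.895 and (1 − 0.125)/(1 − 0.075) = 0.946.

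**Effect of the counting rule.** Simulation used 300 trials per scenario, 82 per arm, four follow-up windows and a true ratio of 1.0. It assumed 0.58 events per year and gamma frailty variance 1. A Poisson GEE with categorical time stood in for the mixed model. Median rate ratios:

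| Dropout MBCT-S / TAU | Unobserved = zero events | Partial windows kept | Complete windows only | Partial windows with offset |
|---|---|---|---|---|
| 20% / 20% | 1.00 | 1.01 | 1.01 | 1.00 |
| 15% / 25% | 1.03 | 0.99 | 0.96 | 0.96 |
| 10% / 30% | 1.15 | 1.05 | 1.00 | 1.00 |
| 30% / 10% | 0.86 | 0.93 | 0.99 | 0.98 |

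The offset column should be 1.00 throughout, so its low of 0.96 shows simulation error of a few hundredths. All columns in a row use the same simulated trials, so ratios within a row are cleaner. For 30% / 10%, keeping partial windows gives 0.934/0.982 = 0.95.

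A direct calculation agrees. Among those who start a window of length L years, the mean observed fraction is (1 − e^(−λL))/(λL), with λ = −ln(1−d).

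- 26-week window: 0.916/0.974 = 0.940.
- 18-week window: 0.941/0.982 = 0.958.
- Each 4-week window: 0.986/0.996 = 0.990.
- Weighted by length: (26 × 0.940 + 18 × 0.958 + 8 × 0.990)/52 = 0.954.

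**Floating windows.** If a window averaged 8 weeks in one arm and 10 in the other, that window's ratio would be multiplied by 0.80 or 1.25. This is an illustration; the documents do not predict such a gap.

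**The case against.** The strongest reply is that nothing in the documents says a partly observed window counts as a full one. A reader might infer that from the missing offset, but the inference does not hold. Section 4.2 measures events with the C-SSRS at each follow-up. A participant who leaves mid-window has no closing interview, so on interview data that row would normally be missing and drop out of the mixed model. With complete windows only, the simulated ratios at 20-point dropout gaps are 1.00 and 0.99. This reply stands. What remains is that the plan does not state the rule, and that chart events could supply counts for windows with no closing interview.

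Two mitigations are real but partial. Block matching aligns the assessment timeline across arms, so an example with a 6-week Time 2 to Time 3 window in one arm and 4 weeks in the other (a factor of 1.5) would run against the plan. If Time 4 stays at 6 months, a longer early window also shortens the next one. Matching does not equalise dropout or late interviews. Chart review covers 12 months for everyone, but section 3 describes the record data as verification, and section 5 does not say that charts fill unobserved time.

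Two further readings also fail. The unequal planned windows do not by themselves bias the comparison of arms if time is categorical. Variation in window length that is alike in both arms adds dispersion, not bias.

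Finally, a short description of a model may simply leave out an offset that the analyst intends. That is possible. But the section names the other terms and deals with unequal follow-up for H1a, so the omission is worth closing in writing.

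**Conclusion.** The point holds as a modest, conditional one. H1b as written has no exposure term and no rule for partial or missed windows. Bias arises only if observed time differs by arm and partly observed or unobserved time stays in the analysis.

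For an assumed 30% against 10% dropout and a true ratio of 1.0, the estimate is about 0.93 to 0.95 with partial windows kept, 0.86 to 0.89 with unobserved time scored as zero events, and about 1.0 with complete windows only. Reversing the arms gives about 1.05 and 1.13 to 1.15 for the first two rules. With dropout gaps of 4 to 10 points, the zero-event rule shifts the ratio by about 2% to 6%. With equal dropout there is no bias. The documents give only 20% overall, so every arm split here is an assumption.

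A reader might infer that the main result is at risk. It is not: time to first event is analysed by Cox regression, which handles unequal follow-up. H1b is a supporting analysis.

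**What to change.** In section 5, under H1b:

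1. Add log(time actually observed in that window for that participant) as an offset.
2. Set the baseline look-back to a defined length, so that the baseline row has an exposure too.
3. Count time as observed only where an interview or chart follow-up covers it, and say which source supplies events for that time.
4. Leave out wholly unobserved windows, for which the offset is undefined.
5. Report event rates and rate ratios.

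The cost is one model term, a few sentences and some data handling to derive person-time from interview and chart dates. The documents do not list interview dates as a data item, but the planned time-to-event analysis needs event and censoring dates, and section 3.5 keeps treatment dates in the extract. No extra participants or visits are needed. The offset does not correct for dropout that is itself related to suicide risk; that needs separate treatment.
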